#### **11.2.3. Overall Survival**

Overall survival is defined as the duration from enrollment date to the date of death from any cause. Subjects who are alive or lost to follow-up at the time of the analysis will be censored at the last known date they were alive.

#### **11.2.4. Overall Response**

Overall response will be determined for each patient as a binary variable indicating whether or not the patient achieved a best overall response of CR or PR as determined by RECIST 1.1 criteria. For the purposes of response determination, a confirmatory scan for CR and PR is not required.

#### **11.2.5. Disease Control**

Disease control will be determined for each patient as a binary variable indicating whether or not the patient achieved a best overall best response of CR, PR, or stable disease as determined by RECIST 1.1 criteria.

#### **11.2.6. Safety Endpoints**

Safety endpoints will include treatment administration (cycles delivered, cumulative dose administration, and relative dose intensity), AEs, SAEs, deaths while on study therapy, and laboratory determinations.

### **11.3. Analysis Populations**

Efficacy and safety analyses will be conducted on the population of subjects who begin regorafenib treatment. Analysis of overall response rate will be conducted on those patients in the efficacy population with measurable disease present at baseline. The date of initiation of regorafenib treatment will be the enrollment date.

## **11.4. Analysis Methods**

### **11.4.1. Timing of Analysis**

While not planned as a formal multistage analysis, we will be evaluating safety and efficacy in data reviews throughout the course of the study. The analysis for the primary objective will occur after all 32 patients have either progressive disease, died, or have at least 16 weeks of follow up time after the treatment start date. Preliminary analysis of the secondary endpoints (including PFS and OS) will also be done at the time of the primary analysis. However, an updated PFS analysis will also occur once the PFS censoring rate for all enrolled patients reaches 20% or after all patients have at least 1 year of follow up time (whichever occurs first). Additionally, for the purposes of OS, patients will continue to be followed until the OS censoring for all enrolled patients reaches 20% or after all patients have at least 3 years of follow up time (whichever occurs first), and the final analysis will be conducted after this milestone is reached.

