### **3.4. Subject Withdrawal**

Subjects **must be** withdrawn from the trial (treatment and procedures) for the following reasons:

- Subject withdraws consent from study treatment and study procedures. A subject must be removed from the trial at his/her own request or at the request of his/her legally acceptable representative. At any time during the trial and without giving reasons, a subject may decline to participate further. The subject will not suffer any disadvantage as a result.

- Pregnancy. Pregnancy will be reported as an SAE. (Note: Subjects who have been withdrawn from treatment with study drug because of pregnancy should not undergo CT scans [with contrast]/MRI or bone scans while pregnant.)
- If, in the Investigator's opinion, continuation of the trial would be harmful to the subject's well-being.
- Subject is lost to follow-up after three consecutive months of attempted contact.
- Death.

Subjects **may be** withdrawn from the study for the following reasons:

- The subject is non-compliant with study drug, trial procedures, or both; including the use of anti-cancer therapy not prescribed by the study protocol.
- Severe allergic reaction to regorafenib (such as exfoliative erythroderma or Grade 3 or 4 hypersensitivity reaction).
- The development of a second cancer.
- Development of an intercurrent illness or situation which would, in the judgment of the Investigator, significantly affect assessments of clinical status and trial endpoints.
- Deterioration of ECOG performance status to 4.
- Use of illicit drugs or other substances that may, in the opinion of the Investigator, have a reasonable chance of contributing to toxicity or otherwise skewing trial result.
- Any other (non-disease related) reason, at the Investigator's discretion.

Any subject removed from the trial will remain under medical supervision until discharge or transfer is medically acceptable.

In all cases, the reason for withdrawal must be recorded in the CRF and in the subject's medical records.

Details for the premature termination of the study as a whole (or components thereof [e.g. centers, treatment arms, dose steps]) are provided in Section 12.2.

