### **4.2. Overall Investigational Plan**

This is a single arm, single stage Phase II study designed to evaluate progression free survival in patients with locally-advanced or metastatic pancreatic cancer who have failed at least one prior line of therapy. This study will initially open at LCI.

Additional investigational site(s) beyond the coordinating site will be added following activation. A total of 32 subjects will be enrolled to this study over a two year accrual period. Following informed consent and eligibility check, all patients will start oral regorafenib therapy and will continue therapy until progression or patient withdrawal. Treatment must start within 7 days of the eligibility date. Subjects will undergo radiological staging after the first two cycles of regorafenib therapy. Subjects with progressive disease as assessed by RECIST 1.1 will be removed from the study. Subjects who have at least stable disease will continue regorafenib therapy, at the Investigator's discretion, and will be radiologically restaged bimonthly. The overall duration of the study is expected to be no longer than 24 months.

Data from this study will be collected on electronic case report forms (eCRFs).

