### **11.5. Interim Analyses**

No interim analyses are planned for this study.

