## **12. STUDY COMPLETION AND TERMINATION**

### **12.1. Completion**

The study will be considered complete when one or more of the following conditions is met:

- All subjects have completed all study visits.
- All subjects have discontinued from the study.
- The IRB, LCI DSMC, Sponsor-Investigator or Bayer HealthCare discontinues the study because of safety considerations.
- The Sponsor-Investigator defines an administrative or clinical cut-off date.

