## **12.2. Termination**

The study will be terminated when one or more of the following conditions occur:

If risk-benefit ratio becomes unacceptable owing to, for example:

- Safety findings from this study (e.g. SAEs)
- Results of any interim analysis
- Results of parallel clinical studies
- Results of parallel animal studies (e.g. toxicity, teratogenicity, carcinogenicity or reproduction toxicity).
- If the study conduct (e.g. recruitment rate; drop-out rate; data quality; protocol compliance) does not suggest a proper completion of the trial within a reasonable time frame.

The Sponsor-Investigator has the right to close the trial at any site and at any time.

For any of the above closures, the following applies:

- Closures should occur only after consultation between involved parties.
- All affected institutions must be informed as applicable according to local law.
- In case of a partial study closure, ongoing subjects, including those in follow-up, must be taken care of in an ethical manner.

Details for individual subject's withdrawal can be found in Section 3.4.

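### Do efficacy data reviews during the study, and a termination example that mentions an interim analysis, undermine the single-stage 8-of-32 test?

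*Combined protocol and SAP*

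**What the plan says.** Section 4.2 describes the design: "This is a single arm, single stage Phase II study designed to evaluate progression free survival". Section 11.1 sets 32 subjects, a null 16-week progression-free rate of 0.15, an alternative of 0.35, a one-sided exact binomial test at 0.10, at least 90% power, and rejection if 8 or more subjects are alive and progression free at 16 weeks. Section 11.4.4.1 repeats the test and the cut-off.

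Section 11.4.1 opens with "While not planned as a formal multistage analysis, we will be evaluating safety and efficacy in data reviews throughout the course of the study". Its next sentence fixes the timing: "The analysis for the primary objective will occur after all 32 patients" have progressed, died or been followed for at least 16 weeks. Section 11.5 consists of one sentence: "No interim analyses are planned for this study".

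Section 3.4 points to Section 12.2 for early closure of the whole study. There, "Results of any interim analysis" appears in a list of examples introduced by the condition that risk-benefit has become unacceptable. The same section adds: "The Sponsor-Investigator has the right to close the trial at any site and at any time". Section 8.1 lists what the monthly monitoring meeting covers, and efficacy is not in that list.

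**The concern.** Two pieces of wording sit awkwardly with a single-stage design. Section 11.4.1 says that efficacy will be looked at during the study, but gives no number, timing or audience for the reviews and does not say that they have no bearing on the test. Section 12.2 refers to results of an interim analysis when Section 11.5 plans none. A reader could combine the two and take the data reviews to be informal interim analyses that may end the trial.

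Two things would be at stake. If a review could declare success early at the nominal level, the type I error would exceed 0.10. If a review could stop the trial for poor results, or end it with fewer than 32 subjects evaluated, power could fall below 90%. The trial is open-label and single-arm, and the endpoint admits progression judged subjectively by the investigator (Section 11.2.1), so it is fair to ask what part the reviews play.

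**Working it through.** **Inputs.** From Section 11.1: n = 32, cut-off 8, null rate 0.15, alternative rate 0.35, one-sided level 0.10, power at least 0.90. From Section 11.4.1: one primary analysis, after all 32 patients. The number and timing of the reviews are not given, so any calculation with repeated looks rests on assumed schedules.

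**1. Reproduce the plan's figures.** With X the number alive and progression free at 16 weeks, P(X ≥ 8) = 1 − Σ C(32, k) p^k (1 − p)^(32 − k), summed over k = 0 to 7.

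- At p = 0.15: 1 − 0.9042 = 0.0958, within 0.10.
- At p = 0.35: 1 − 0.0818 = 0.9182, above 0.90.

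Neighbouring cut-offs fail: 7 gives a type I error of 0.195, and 9 gives power of 0.842. With 31 subjects and a cut-off of 8, power is 0.8991, so 32 is the smallest sample size that meets both limits. The design is right as stated.

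**2. Does the text let a review change the test?** Read in order, the sections answer this.

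- 4.2: single stage.
- 11.1 and 11.4.4.1: one rule, on 32 subjects.
- 11.4.1: the reviews are introduced as not being a formal multistage analysis, and the next sentence puts the primary analysis after all 32 patients.
- 11.5: no interim analyses.
- 12.2: closure examples, with the interim-analysis one under an unacceptable risk-benefit ratio.

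None of these allows an early claim of efficacy or applies the cut-off to fewer than 32 subjects. Followed as written, the figures in step 1 are the operating characteristics of the trial.

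**3. Would looking, or stopping once the result is settled, alter the error rates?** Looking without acting changes nothing. Stopping when the outcome of the 8-of-32 rule is already certain also changes nothing, in either direction:

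- Failure is certain once 32 − 8 + 1 = 25 subjects have failed. Exact enumeration with a stop there returns 0.0958 and 0.9182.
- Success is certain once 8 subjects have succeeded. Exact enumeration with a stop there also returns 0.0958 and 0.9182.

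**4. What would it take to do harm?** The schedules below are assumed; none is in the plan.

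| Assumed use of reviews | Type I error at 0.15 | Power at 0.35 |
|---|---|---|
| Early success claim at nominal 0.10, looks at 16 and 32 | 0.132 | 0.929 |
| Same, looks at 11, 22 and 32 | 0.160 | 0.937 |
| Same, looks at 8, 16, 24 and 32 | 0.141 | 0.932 |
| Same, after every subject from 8 to 32 | 0.190 | 0.945 |
| Stop for poor results at 1 or fewer of 16 | 0.095 | 0.915 |
| Stop for poor results at 2 or fewer of 16 | 0.088 | 0.897 |

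Inflation needs an early success claim, which the plan does not provide. Stopping for poor results can only lower the type I error, and the power it costs depends on a rule that the plan does not contain.

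**The case for a change.** The strongest case for a change is that saying the reviews are not a formal multistage analysis tells the reader what they are not, and leaves open what they are. The stated power depends on all 32 subjects being evaluated: at the exact 0.10 level, fixed sizes of 31, 27 and 22 give power of 0.899, 0.885 and 0.837. The sponsor-investigator sees the data as they accrue and may close the trial at any time. Section 12.2 then mentions an interim analysis, so either the example refers to nothing or the Section 11.4.1 reviews are that analysis and Section 11.5 is inexact. One sentence would answer a question that readers of the final report may ask.

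The textual part stands: the word descriptive is absent, and the example in Section 12.2 has no planned counterpart. The consequence does not follow. The power losses at 31, 27 and 22 would affect any trial that ended short of its target, for whatever reason, and do not come from this wording. A broad right to close a trial is no licence to test early. The Section 12.2 example is generic (any interim analysis, offered as an example and tied to risk-benefit), and it is compatible with none being planned. Section 12.1 and Section 12.2 allow closure on several grounds, including an administrative cut-off and poor recruitment, so nothing here depends on closure being confined to safety.

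**Conclusion.** No change to the plan is needed. The missing label on the reviews is a gap that an analyst fills correctly from the adjacent sentence and from Sections 4.2, 11.1 and 11.5: summaries seen before the primary analysis are descriptive, and the 8-of-32 rule is applied once, to all 32 patients. The example in Section 12.2 is stock wording with no operative effect.

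The size of the problem for the plan as written is zero: exact type I error 0.0958 and power 0.9182, with sample size, cut-off and reported estimates the same whether or not the wording is tidied. This rests on two assumptions: the primary test is run once, when Section 11.4.1 says, and no data review is used to claim success early. Using the reviews for an early claim would depart from Sections 11.4.1 and 11.5, and under the assumed schedules above the type I error would then lie between about 0.13 and 0.19.

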### **11.4.2. Subject Disposition**

An accounting of all consenting subjects will be provided at the end of the study. This will include a breakdown of subjects who consented, were treated, discontinued treatment, died, and were lost to follow-up or withdrew consent.

### **11.4.3. Baseline Subject and Disease Characteristics**

A summary of subject demographics and disease-related characteristics will be completed and subject medical history will be assessed.

### **11.4.4. Efficacy Analyses**

#### **11.4.4.1. Primary Analysis**

The frequency and proportion of subjects alive and progression free

after 16 weeks will be calculated, along with a 95% Clopper Pearson confidence interval. A one-sided exact binomial test of proportions, with  $\alpha = 0.10$ , will be carried out, testing the null hypothesis that the 16-week progression free survival probability is less than 15%. Based on the sample size calculations described in Section 11.1, if at least 8 subjects are alive and progression free at 16 weeks, the null hypothesis can be rejected.

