G. Inclusion/Exclusion	
 
-Histologically or cytologically-proven metastatic adenocarcinoma of the exocrine pancreas.
 
-Life expectancy of at least 8 weeks.
 
-ECOG Performance Status 0 – 2.
 
-Subjects must have previously undergone at least one documented line of chemotherapy for advanced disease and have had prior treatment with gemcitabine either as part of adjuvant therapy or for advanced disease.
 

H. Dosage, Route, and Dose Regimen	Subjects will take 120 mg oral regorafenib (tablets) once daily (with a low-fat breakfast) for cycle 1. If well tolerated, the daily dose will be escalated to 160 mg daily. Dose reductions will follow protocol guidelines regardless of whether subject is dose escalated or not. Each cycle is 28 days, with daily dosing for 21 days, followed by a 7 day break.
I. Statistical Analysis	The frequency and proportion of subjects alive and progression free after 16 weeks will be calculated, along with a 95% Clopper-Pearson confidence interval. A one-sided test of proportions, with $\alpha = 0.10$ , will be carried out, testing the null hypothesis that the 16-week progression free survival probability is less than 15%.

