## 11. STATISTICAL CONSIDERATIONS

### 11.1. Sample Size

A total of 32 participants will be enrolled to this study. The primary objective is to evaluate the 16-week progression free survival rate. The CONKO-003 study reported a median OS with best supportive care in this subject population to be 2.3 months. Therefore, the null hypothesis assumes a median PFS of 6 weeks. This corresponds to a 16-week PFS rate of approximately 0.15. A single-stage design will be used to test the hypothesis that the 16-week PFS rate is less than or equal to 0.15. If at least 8 of the 32 subjects are alive and progression free at 16 weeks, the null hypothesis will be rejected (based on an exact binomial test) and regorafenib therapy may be considered for further evaluation in this subject population. Assuming a one-sided alpha = 0.10 significance level, this sample size will provide at least 90% power to reject the null hypothesis, assuming the true 16-week progression free survival rate is 0.35. An increase in the 16-week PFS rate of 0.20 in the context of this Phase II study is considered clinically relevant.

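### Does a 95% confidence interval beside a one-sided 0.10 test leave the primary result ambiguous at 8 or 9 successes out of 32?

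*Combined protocol and SAP*

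**What the plan says.** Section 11.1 sets the design. The hypothesis is stated as "A single-stage design will be used to test the hypothesis that the 16-week PFS rate is less than or equal to 0.15", the size as "A total of 32 participants will be enrolled to this study", and the operating characteristics as "Assuming a one-sided alpha = 0.10 significance level, this sample size will provide at least 90% power to reject the null hypothesis". The alternative behind that power figure is a rate of 0.35. The decision is a count: "If at least 8 of the 32 subjects are alive and progression free at 16 weeks, the null hypothesis will be rejected", and the same sentence says that this is based on an exact binomial test.

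Section 11.4.4.1 gives the analysis. The number and proportion of successes are to be reported "along with a 95% Clopper Pearson confidence interval. A one-sided exact binomial test of proportions" at alpha 0.10, and the cut-off is repeated: "if at least 8 subjects are alive and progression free at 16 weeks, the null hypothesis can be rejected". Item I of the Protocol Summary has the same pairing, with the estimate reported "along with a 95% Clopper-Pearson confidence interval".

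Neither place writes two-sided beside the interval, though that is the ordinary reading of a Clopper-Pearson interval. No 80% or 90% interval and no one-sided bound is planned for the primary endpoint, and nothing says how the interval should be read against the test. Section 11.4.4.2 uses the same 95% Clopper-Pearson method for the response and disease control rates.

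**The concern.** Readers often use a confidence interval as a second view of the test: if the null value lies inside, they expect no rejection. That holds only when the interval's tail area equals the test's significance level. Here the test spends 10% in the lower tail and a two-sided 95% interval spends 2.5%, so near the cut-off the two can appear to disagree.

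The disagreement falls on the protocol's own boundary. A trial with exactly 8 successes would reject 15% and, in the same sentence, report an interval reaching down to 11.5%. If the plan did not say which result governs, the choice would be made after the data were seen, and the further evaluation of regorafenib that section 11.1 ties to rejection could be disputed. The remedy would be to make the two-sided 80% interval, or equivalently the one-sided 90% lower bound, the interval tied to the decision, and to label the 95% interval descriptive.

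**Working it through.** **Inputs.** From section 11.1: n = 32, null rate 0.15, alternative 0.35, one-sided alpha 0.10, power at least 90%, reject at 8 or more. From section 11.4.4.1: exact binomial test and 95% Clopper-Pearson interval. Assumption: the interval is two-sided, so each tail is 2.5%.

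**Step 1: the plan's own figures.** With X binomial(32, p):

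- P(X ≥ 8 | p = 0.15) = 0.0958, within 0.10.
- P(X ≥ 7 | p = 0.15) = 0.195, so 8 is the smallest valid cut-off.
- P(X ≥ 8 | p = 0.35) = 0.918, above 0.90.

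The stated rule, alpha and power all reproduce.

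**Step 2: intervals by count.** For x successes and tail area a, the lower limit is the a quantile of Beta(x, n − x + 1) and the upper limit is the 1 − a quantile of Beta(x + 1, n − x). Use a = 0.025 for the 95% interval and a = 0.10 for the 80% interval, whose lower limit is the one-sided 90% bound.

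| Count | One-sided p | Test rejects 15%? | 95% interval | 80% interval |
|---|---|---|---|---|
| 7/32 | 0.195 | no | 9.3% to 40.0% | 12.6% to 34.0% |
| 8/32 | 0.096 | yes | 11.5% to 43.4% | 15.1% to 37.4% |
| 9/32 | 0.041 | yes | 13.7% to 46.7% | 17.7% to 40.7% |
| 10/32 | 0.016 | yes | 16.1% to 50.0% | 20.4% to 44.0% |

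The 95% interval first excludes 15% at 10/32, and the test first rejects at 8/32. The mismatch is therefore at 8 and 9 only. The 80% lower limit passes 15% between 7 and 8, exactly where the test does.

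**Step 3: how often it would occur.**

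| True rate | P(X = 8 or 9) | P(X ≥ 8) | Share of rejections |
|---|---|---|---|
| 0.15 | 0.080 | 0.096 | 84% |
| 0.25 | 0.304 | 0.568 | 54% |
| 0.30 | 0.283 | 0.788 | 36% |
| 0.35 | 0.187 | 0.918 | 20% |

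The 84% is conditional on a false rejection, which itself has a probability of 9.6%. Over all trials at a true rate of 0.15, the mismatch occurs in 8.0%.

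**Step 4: what a matched interval would add.** By construction the one-sided 90% lower bound exceeds 15% if and only if the count is 8 or more. It gives the decision that the count already gives. A two-sided 90% interval would not remove the mismatch, since its lower limit is 13.1% at 8/32 and 15.5% at 9/32.

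**Sensitivity to the two-sided reading.** If the 95% interval were read as a one-sided 95% bound, its lower limits would be those same 13.1% and 15.5%. The mismatch would then remain at 8/32 alone.

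**The case for a change.** The strongest case for a change is that this is a likely outcome. At the design alternative, roughly one trial in five would land on 8 or 9, and at true rates of 0.25 to 0.30 it would be close to three in ten. A reader who applies the usual correspondence between intervals and tests would take such a trial as negative. The protocol gives no reading guidance, and a single sentence written before the data would forestall the argument at almost no cost.

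The arithmetic stands, and so does the observation that the interval is not labelled descriptive. The claim that a reader cannot tell which result governs does not stand. The plan states twice that success is a count of at least 8, and section 11.1 bases that on the exact test. No passage gives the interval a role in the decision, so no outcome leaves the conclusion open and there is nothing to choose after the fact.

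Nor do the two results contradict each other. At 8/32, 15% is rejected at the 10% level and not excluded at the 2.5% level. Both statements are true, and the plan states both the test's alpha and the interval's confidence level. The 95% interval is also the level used for the plan's other binary rates, and it gives readers the conventional measure of precision.

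**Conclusion.** No change follows, because a change would gain nothing. Followed as written, the plan gives a valid test (alpha 0.0958, power 0.918), a valid 95% interval estimate and a decision fixed in advance by count. The mismatch is confined to 8/32 and 9/32 on the two-sided reading, with probability 18.7% at a true rate of 0.35 and 8.0% at 0.15. A matched bound would alter no decision, error rate, sample size or data item.

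Whether to print the one-sided 90% lower bound (15.1% at 8/32) beside the 95% interval is a matter of presentation. If the count does fall on 8 or 9, the analyst can say in the report that the decision rests on the exact test at 0.10 and that the 95% interval describes precision. The plan already supports that statement. The conclusion assumes that all 32 subjects are in the denominator, as the stated cut-off requires.
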